## **11. SAMPLE SIZE JUSTIFICATION AND STATISTICAL ANALYSIS:**

This is an exploratory, descriptive study for an orphan disease. The sample size is based on the prevalence of the disease and the availability of the subjects for the study. Based on our clinic numbers and expected numbers of subjects who will travel for this study, we expect 60 subjects to qualify for the study.

We will also perform analysis of responders vs. non-responders, taking multiple measurements for placebo patients into account, treating the patient as random effect, adjusting for age, sex and possibly other markers.

One of the potential trigger points to stop this study will be if milestones are reached that document statistically significant beneficial effect of sildenafil requiring no additional placebo treated subjects, or possibly no beneficial effect. We have reviewed the details of our study with our biostatistician. Because this is a very early study, we are unable to estimate the response to therapy and develop an effect size. For that reason we will do an interim analysis after completion of the first 15 subjects, 10 treated with sildenafil for the first 20 weeks and 5 treated with placebo for 20 weeks. We will evaluate the first 15 subjects for efficacy and futility and add to this analysis each additional 15 subjects as they complete the study. We should be able to use the interim analysis to project effect size and estimate the total number of subjects required for the study. If after analysis of 15, 30 or 45 subjects we find that we are in the range of futility or efficacy, then we will notify the FDA as well as the DSMB, and begin to end the study by adding no additional subjects.

We will include in the interim analysis information about the characteristics of LMs. We will do a sub-analysis looking at specifics of location, lesion type (microcystic,

macrocystic, or mixed and percent macrocystic), as well as previous procedures, infections or other interventions. If this process documents characteristics of lesions that do or do not respond to sildenafil, we will reconsider our study entry criteria and submit a protocol amendment, focusing on specific characteristics of which type lesion a subject should have in order to be enrolled in the trial.

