## 2. SYNOPSIS

Study Phase: 2

Financial Disclosure Information for U.S. FDA Submission to be Obtained? Yes

Test Medication: Sildenafil 20 mg tablets, 2.5mg/ml suspension (Revatio®)  
Control Medication: Placebo tablets or suspension resembling Revatio®

Study Dosage / Usage: Oral dosage of sildenafil. For pediatric patients 8 kg to 20 kg the suspension/tablets dose will be 10 mg/4ml three times a day (30 mg per day) and for patients > 20 kg the dose is 20 mg/8ml three times a day (60 mg a day). Subjects less than 8 kg will not be enrolled in the trial.

Route of Administration: The medication will be given orally. The subjects who will receive the 10 mg dose will be given an oral suspension (using dose calculation by the study pharmacist) or half a tablet. Subjects will have the option of taking tablets or receiving an oral suspension of the medication in 2.5mg per mL.

Objective(s): The objectives of this study are to assess the safety and effectiveness of sildenafil taken orally to improve or resolve lymphatic malformations.

Study Population: Sixty Subjects (60)

Subjects will be between the ages of 6 months to 10 years of age inclusive with lymphatic malformations (LM) that have a **minimum diameter of 3 centimeters** based upon MRI evaluation. Based on the patient numbers in pediatric dermatology clinics over the country, we expect that we will be able to screen 60 patients who will meet the inclusion criteria, and 55 patients will be enrolled in the study and begin medication. After 15 subjects are completed, an interim analysis will be performed to project effect size and estimate the total number of subjects required for the study. If after analysis of 15, 30 or 45 subjects we find that we are in the range of futility or efficacy, then we will notify the FDA as well as the DSMB, and begin to end the study by adding no additional subjects.

Structure: Double-blind trial of placebo compared to sildenafil with an open label extension for subjects who received placebo. Two to one ratio of two sildenafil treated subjects who

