### 7.4.3. Lymphatic malformation assessment

The most precise method of lymphatic malformation evaluation will be the MRI examination. Clinical assessment of each lymphatic malformation includes measuring the hemicircumference of the lesion by using a soft measuring tape placed on the skin over the area of the widest diameter of the lesion. The investigators will be fully trained in the standardized methods to obtain these measurements. We have found in our preliminary subjects that the investigators vary in their measurement of length, width and hemispheric measurement unless they practice these measurements together in order to standardize their methods. The length, and width, will then be calculated as described in Figure 2 of Berk et al.(Berk, Berk et al. 2011) We will use linear mixed model to compare the changes in volume over time between and within subjects who receive placebo and those who receive sildenafil. In order to document the site of the measurements a diagram will be drawn by hand or photographs will be taken of the methods. Each clinic visit will try to duplicate the measurements methods used in the initial visit.

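### Enrolment can close for benefit or futility at 15, 30 or 45 subjects with no stated alpha, boundary or deciding analysis, and a first look of 10 vs 5 is far too imprecise to project an effect size or total N

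*Combined protocol and SAP*

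**What the plan says.** Section 11 names as a potential reason to stop that "milestones are reached that document statistically significant beneficial effect of sildenafil requiring no additional placebo treated subjects", or possibly an absence of benefit. The operating rule, in both the Synopsis and Section 11, begins "If after analysis of 15, 30 or 45 subjects we find that we are in the range of futility or efficacy". In that event the FDA and the DSMB are notified and the team will "begin to end the study by adding no additional subjects". The looks are cumulative: after the first 15 subjects (10 sildenafil, 5 placebo) the plan will "add to this analysis each additional 15 subjects as they complete the study".

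The first look has a second job. Section 11 says that no effect size can be given in advance, and then: "We should be able to use the interim analysis to project effect size and estimate the total number of subjects required for the study". If lesion characteristics appear to predict response, "we will reconsider our study entry criteria and submit a protocol amendment".

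On analysis methods:
- Section 10.2.1 (Primary Efficacy) gives only summary statistics for MRI volume change.
- Section 7.4.3 says "We will use linear mixed model to compare the changes in volume over time between and within subjects", but inside the paragraph on tape measurements, so it is unclear whether this covers MRI volume.
- Section 11 adds: "We will also perform analysis of responders vs. non-responders, taking multiple measurements for placebo patients into account, treating the patient as random effect".

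None of these is named as the test for the interim looks. Section 9 refers DSMB details to a Safety Monitoring Plan held in the IND, which is not among the supplied documents.

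The maximum is not one number. The Synopsis expects 55 subjects to start medication, Section 6.1 enrols 60, and Section 5.1 aims for 40 who complete 20 weeks with an MRI.

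**The concern.** A rule that can close recruitment on significance, applied at up to three interim looks and a final analysis, needs a stated overall error rate and a boundary fixed beforehand. Without them, three things are at risk.

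1. Repeated testing at a conventional level raises the chance of closing enrolment for a benefit that does not exist.
2. Closing enrolment does not end data collection. Subjects already randomised would presumably finish, so there will be two results, one at the look and one on the complete data. The plan does not say which counts.
3. A stop at 10 vs 5 needs a very large observed difference, so the effect reported after such a stop is too high on average. A sample size built on that look could be far too small or have no finite value.

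A boundary chosen after the first look has been seen would not be credible, so the timing matters.

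**Working it through.** The documents state no alpha, power, effect size, SD or boundary, so there is no figure of the plan's own to reproduce.

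**Inputs from the documents.** Looks at 15, 30 and 45 (Synopsis, Section 11); 2:1 allocation (Synopsis); first look 10 vs 5 (Section 11); maximum 60, 55 or 40 (Sections 6.1, 2, 5.1).

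**Assumptions.** Two-sided 5% pooled t-test between arms at each look; normal data; blinded-period data only; no futility stop. With two MRIs per subject, complete data and no covariates, the arm-by-time term of a random-intercept mixed model gives the same statistic as this t-test.

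**Step 1. False benefit when each look is tested at 5%** (simulation under no effect, benefit direction only, against 2.5% for one test).
- Cumulative wrong stop: 2.5% at 15, 4.2% by 30, 5.4% by 45.
- Wrong stop or final claim: 6.4% (maximum 60), 6.2% (55), about 5.3% (looks at 15/30/40).
- Binding futility lowers the 6.4% only to 6.2% (stop if t<0) or 5.6% (stop if t<0.5).

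**Step 2. If the complete data decide.** Overrun = lag in weeks x 60 / accrual weeks. Accrual is not in the documents; take 200, 133 or 80 weeks.
- 20-week lag: 6, 9 or 15 subjects.
- 32-week lag (end of study): about 10, 14 or 24.
- 52-week lag (placebo subjects who cross over): about 16, 23 or 39.

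After a benefit stop, add the overrun, capped at 60, and retest at 5%:

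| Overrun | False final claim |
|---|---|
| 6 | 3.9% |
| 9 | about 3.5% |
| 15 | 3.0-3.1% |
| 24 | about 2.8% |
| 39 | about 2.6% |

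The share of false early stops no longer significant is about 46% with 6 overrun subjects, 53% with 9 and 61% with 15, and about 71% with 39. The 5.4% chance of wrongly closing enrolment is the same whatever the overrun.

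**Step 3. First look, 10 vs 5.**
- SE = sqrt(1/10 + 1/5) = 0.548 SD.
- Critical observed effect = t(0.975, 13 df) x 0.548 = 2.160 x 0.548 = 1.18 observed SD.
- An observed 0.8 SD has a 95% interval of 0.8 ± 1.18 = -0.38 to 1.98 SD (-0.33 to 1.90 by noncentral t).
- At 2:1 the variance of the difference is 4.5 SD²/N, so for 80% power N = 4.5 x ((1.96 + 0.84)/d)². At d = 0.8, N = 4.5 x 12.25 = 55. At d = 1.98, N = 9. At d of zero or below there is no finite N.
- At a true 0.5 SD, a benefit stop at 15 occurs in 13% of trials. The mean estimate among those stops is 1.32 true SD, 2.6 times the truth (1.32/0.5).

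**Step 4. What a boundary would do** (maximum 60).
- O'Brien-Fleming-type spending (nominal p 0.000015/0.0030/0.018/0.044), or p<0.001 at each interim look and 0.049 at the end, both hold false benefit at about 2.5%.
- Testing all randomised subjects at the last nominal p after an overrun of 6-15 gives 2.1-2.4% (spending) or 2.4-2.5% (p<0.001).
- At an assumed true 0.78 SD, one test at 60 has 80.0% power and the spending rule 79.2%, or about 78% if the benefit must also hold after overrun. The unadjusted rule with overrun has 75.7-76.7%.
- Mean N at stopping at 0.78 SD, before overrun: 37 (unadjusted), 50 (spending), 56 (p<0.001).

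**The case against.** The strongest case against has five parts.

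- **The 5% per look is not in the documents.** This stands. A reader might infer that the plan tests each look unadjusted at 5%. It does not say so; it says nothing about the level. The error rates illustrate one conventional reading of the stopping trigger.
- **A stop is not a claim.** This stands too. A reader might take 5-6% as the rate of false efficacy findings. It mixes wrongful closure of enrolment with final claims. If the complete data decide, the false-claim rate is about 2.6-4%. It is nearer the lower end if looks wait for week 32 or later, which the Section 11 wording on later looks allows.
- **The rules may sit in the Safety Monitoring Plan.** Possible. The documents do not support saying that no rules exist anywhere, only that the protocol and SAP text contains none and cites none for these looks.
- **The study is Phase 2 and labelled exploratory and descriptive, with N set by availability.** This lowers the severity but does not remove the gap, because the same section makes significance a trigger for closing enrolment.
- **A boundary delays stopping.** This stands. A reader might think the fix costs no patients. It needs none beyond planned enrolment, but mean N at stopping rises by 13 to 19 at 0.78 SD.

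It would also be too strong to say that the first look tells nothing about effect size. It gives an estimate, but one far too imprecise for the use proposed.

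**Conclusion.** The concern holds in this form, as something that should be fixed and settled before the first look. The supplied documents let enrolment close on an unspecified criterion and leave open which analysis decides.

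Under an assumed two-sided 5% t-test at each look, wrongful closure for benefit is about 5.4% over three looks, and a wrong stop or final claim about 5-6%, against 2.5%. With complete data deciding, the false final claim is about 2.6-4% for an overrun of 39 down to 6 subjects, and about 45-71% of false stops would be contradicted by the trial's own final data.

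The first-look imprecision does not depend on the 5% assumption: it follows from 10 vs 5 alone.

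The figures exclude the covariates, the placebo-to-sildenafil MRI comparison and any change of entry criteria after the first look. Under the 40-completer goal, a look at 45 completers might never occur.

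**What to change.** Before the first look, amend Section 11 and the Synopsis as follows.

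1. Name the primary MRI test and one overall two-sided 5% level. Pre-specify an error-controlling boundary with non-binding futility, with information measured in week-20 MRI completers against one stated maximum. Either rule in Step 4 would serve; recalculate the nominal values for the final model and look schedule. If the Safety Monitoring Plan already holds such rules, cite them.
2. State that the analysis of all randomised subjects, including those still on treatment at a stop, decides the result, and at what level.
3. Reconcile 55 (Synopsis), 60 (Section 6.1) and 40 completers (Section 5.1) with the looks at 15, 30 and 45.
4. Do not set N from the first-look effect. If N is re-estimated, use the pooled SD and a pre-stated worthwhile difference, capped at planned enrolment, and report the imprecision: with 13 df the estimated N runs from 0.39 to 1.90 times the true requirement (95% range).

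The cost is wording and, with the spending boundary at an assumed 0.78 SD and 60 completers, about one point of power (80% to 79%). Stopping comes later: mean N at stopping, before overrun, rises from about 37 to about 50 (spending) or 56 (p<0.001). That is within planned enrolment, with about a third of the added subjects on placebo. A stop for efficacy at 15 becomes rare (0.04% with spending, 1.7% with p<0.001, at 0.78 SD).

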receive active sildenafil to one placebo treated subject. During the twenty week evaluation visit, after completion of all evaluations, the randomization code will be broken and both the subject and investigator will know the results. The subjects who have randomized to placebo will have the option to begin a twenty week course of sildenafil. If the subjects who were on placebo elect to take active drug, the initiation visit can be completed at that time. The subject will then be followed with clinic visits at weeks 4, 12, 20 and 32 as indicated in the protocol. We will call the subjects at weeks 2, 8 and 16 to inquire about any questions that the subjects may have or any concerns. We will also request information on medication taken and their progress.

The subject's LMs will be categorized by the Pediatric Radiologist by the percent of the LM that is microcystic. Upon completion of the initial 15 subjects, the data will be evaluated in an interim analysis in order to determine if the percent of macrocystic component of the lesions suggests which subjects may have the best benefit. The initial 15 subjects will also be evaluated related to previous procedures, infections and other complications related to their lymphatic malformations. If specific characteristics of the LM are identified that suggests beneficial effect of the sildenafil, the protocol will be changed to enroll those subjects who are projected to have the best benefit. A new power analysis will be done to project the minimum numbers of subjects that should be enrolled further in the study.

Duration of Treatment: 20 weeks. Placebo subjects will complete 20 weeks of placebo and then have an option for 20 weeks of active sildenafil.

Duration of Assessment: The subjects will be evaluated for 20 weeks on therapy then followed for 12 weeks off therapy.

Open Label Extension: Placebo subjects will have an option to enter an open label treatment after they have completed 20 weeks of placebo.

Duration of treatment: Placebo 20 weeks  
Washout Between Periods: none  
Duration of Treatment: 20 weeks on active drug

After the completion of 20 weeks of sildenafil and 12 weeks of follow up, the subjects will have the option to be followed through an IRB approved long-term follow up trial not

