covered in this IND application. That IRB trial would allow up to five years follow up on subjects and would only allow investigators to observe how the subject is doing long term, whichever treatment options the subject pursues in consultation with their regular doctor in that time. That planned follow up protocol will allow Stanford to contact the subjects several times a year in order obtain information about any therapy they may elect to follow, including sildenafil if their regular doctor prescribes it, and their response to any therapy.

Multi-Center:

Yes

Number of Centers:

Up to 4

Blinding:

|                |     |
|----------------|-----|
| Observer-Blind | Yes |
| Subject-Blind  | Yes |
| Double-Blind   | Yes |

Randomization:

Group Assignment Ratio: 2:1 randomization of two subjects who receive sildenafil to one subject who receives placebo.

Concurrent Control:

No other treatments for lymphatic malformation will be allowed except antibiotics and/or surgical drainage if the lesions become infected. Treatment for recurrent infections in the lymphatic malformation will be allowed and documented during the trial. Concurrent medications will be documented. Subjects who require sclerosing agents or excisional surgery of their lymphatic malformation will be withdrawn from the trial.

Variable(s): PRIMARY: Change in lesion volume over twenty weeks of the test medication as evaluated by MRI examination. Comparison of placebo to sildenafil treated subjects.

SECONDARY: Change in lesion volume estimated using a soft tape measure to measure the length, width, and hemispheric measurement of each of the lymphatic malformations. (Berk, Berk et al. 2011) Completion of the form *Lymphatic Malformation Measurements*.

Subject's evaluation of the change in lesion clinical characteristics from baseline to 20 weeks by examining decreased discomfort, texture or thickness, distortion of normal anatomy or overall change obtained in the subject's

completion of *Subject's Assessment of Lymphatic Malformation Change* form.

Physician's evaluation of the lesion clinical characteristics on the day of the visit. This includes color, tenseness and texture, superficial component, deep component, and distortion of anatomical landmarks. This requires completion of the *Lymphatic Malformation Assessment* form for each LM site.

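### Estimating the total sample size from the effect seen in 10 versus 5 subjects is too imprecise; with about 60 subjects available, the practical harm is undersizing after a lucky start.

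*Combined protocol and SAP*

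**What the plan says.** Section 11 bases the sample size on how rare the disease is and how many subjects can travel, and expects 60 to qualify. It then states that, this being an early study, "we are unable to estimate the response to therapy and develop an effect size". For that reason an interim analysis follows the first 15 subjects, "10 treated with sildenafil for the first 20 weeks and 5 treated with placebo for 20 weeks", and the team expects to "use the interim analysis to project effect size and estimate the total number of subjects required".

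The synopsis, under Study Population, fixes the timing: "After 15 subjects are completed, an interim analysis will be performed to project effect size and estimate the total number of subjects required".

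Section 11 also plans to "add to this analysis each additional 15 subjects as they complete the study", with efficacy and futility considered at 15, 30 and 45 subjects. The primary variable in the synopsis is "Change in lesion volume over twenty weeks of the test medication as evaluated by MRI examination", compared between arms. Section 6.1 states that 60 subjects will be enrolled; Section 5.1 gives a goal of 40 who complete 20 weeks and an MRI, with up to 60 enrolled.

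For the projection, the documents give no target difference, SD, significance level, power, lower limit on size, or way of allowing for the imprecision of the estimate.

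**The concern.** A sample size computed from an observed effect varies as one over that effect squared, so moderate noise in the effect becomes very large noise in the size. With 5 placebo subjects the noise is not moderate. A chance large difference at 15 subjects makes the trial look nearly finished; a chance small one makes it look unachievable. Because enrolment is limited to about 60, the second error mostly leaves the trial at its ceiling, while the first can be acted on by enrolling fewer.

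At stake is a trial in a rare paediatric disease ending with too few subjects to show a real reduction in lesion volume. Moreover, if the data that prompted the shrinkage are then tested as though the size had been fixed, chance benefits are locked in more often than the nominal rate.

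**Working it through.** **Inputs from the documents.** Interim of 10 versus 5 (Section 11); 2:1 allocation (synopsis); 60 subjects (Sections 6.1 and 11); 40 completers (Section 5.1).

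**Assumptions.** True standardised effect d from 0.5 to 1.5; normal volume change with equal SD in the arms; all 15 week-20 MRIs available; 80% power and two-sided 0.05 where an absolute size is quoted.

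**The plan's own figure.** The 60 cannot be reproduced, because it rests on availability and no power inputs are given. For orientation, at 2:1 and 80% power, 60 subjects detect d = 0.77 and 40 detect d = 0.94.

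**Step 1, precision.** SE of the standardised difference = √(1/10 + 1/5) = 0.548. An observed effect of 0.8 SD has a 95% interval of about −0.33 to 1.90.

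**Step 2, required size.** At 2:1, N = 4.5 × (1.96 + 0.84)² / d². At d = 0.8 this is 4.5 × 7.84 / 0.64 = 55 (57 in whole 2:1 blocks). At d = 0.5 it is 141.

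**Step 3, error in the projection.** Projected N / true N = (d / d_hat)², so significance level and power cancel. The projection is off by more than two-fold when d_hat lies outside d/√2 to d√2. At d = 0.8 the limits are 0.566 and 1.131. Treating the SD as known:
- lower side: (0.566 − 0.8)/0.548 = −0.43, probability 0.33;
- upper side: (1.131 − 0.8)/0.548 = 0.60, probability 0.27;
- total: 61%.

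**Step 4, SD estimated on 13 df.** Simulated interims, with no cap. An estimate favouring placebo gives no finite N and is counted as above twice the need.

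| True effect (SD) | Below half the need | Above twice the need (wrong sign within this) | Off by more than two-fold |
|---|---|---|---|
| 0.5 | 37% | 39% (18%) | 76% |
| 0.8 | 30% | 33% (7%) | 63% |
| 1.0 | 26% | 29% (3%) | 56% |
| 1.2 | 23% | 26% (1%) | 49% |
| 1.5 | 20% | 22% (under 1%) | 42% |

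The 50% point is d = 1.05 with the SD known and about 1.18 with it estimated. Over the effects that 40 to 60 subjects can detect with 80% power (0.94 down to 0.77 SD), the chance of a more than two-fold error is 58% to 64% with the SD estimated.

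**Step 5, with the enrolment limit.** Size held between 15 and 60, wrong-sign cases continuing to 60, ordinary two-sided 0.05 t-test at the end:
- d = 0.8: power about 77%, against 82% if all 60 are always enrolled; 30% of projections are still below half the need and none is above twice it.
- d = 0: false claims of benefit about 3.7%, against 2.5%, before counting the separate looks at 15, 30 and 45.

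**Step 6, the alternative.** Fix the target difference and estimate only the SD from all 15 subjects without using the arm. At d = 0.8 the resulting size is off by more than two-fold in about 8% of interims, against 63%. Its median is about 10% too large, because the pooled SD absorbs part of the treatment difference.

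**The case against.** The strongest reply is that Section 11 only voices an expectation. It speaks of projecting and estimating, states a size that rests on availability, calls the study exploratory and descriptive, and adds data at 30 and 45. All of that is in the text. A reader might infer that the total will be set by the 15-subject result; the documents do not say the projection is final or binding. Later updating helps but does not remove the problem: at 0.8 SD the chance of a more than two-fold error is still 47–49% at 30 subjects and 38–40% at 45. The exploratory label does not dispose of it either, since the same section would end enrolment on a statistically significant benefit.

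Four other strong readings are tempting and do not stand.
- **That the projection is usually wrong by more than two-fold, whatever the truth.** This fails above about 1.1 to 1.2 SD, and no effect size is given that would exclude so large an effect.
- **That the trial may balloon.** At 0.8 SD the upper quartile of the projection is 184 and the 90th percentile about 3,500, but the latter depends on counting wrong-sign estimates as unbounded (about 900 if sign is ignored). Neither could be acted on with about 60 subjects.
- **That the synopsis repeats the rule under Structure.** The sentence "A new power analysis will be done to project the minimum numbers of subjects that should be enrolled further in the study" follows a conditional narrowing of entry to likely responders, which is a different step.
- **That the final test loses its nominal error rate.** No final test or significance level is specified; Section 10.2.1 promises summary statistics. The 3.7% holds only if an ordinary t-test is used.

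Abandonment after an unlucky start would come from the futility looks, not from this projection.

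**Conclusion.** The point holds in limited form. The plan names a method, an effect estimated from 10 versus 5 subjects, that cannot size this trial with useful accuracy. For true effects up to about 1.1 SD, the uncapped projection is more likely than not off by more than two-fold. Within the available 60, the harm is undersizing: at 0.8 SD, a 30% chance of a projection below half the need and about 5 points of power lost. The two-fold probabilities depend on the assumed true effect, normality and complete MRIs; skewed volumes or missing scans would probably make them worse. The capped results also depend on the assumed floor of 15, the cap of 60 and the final t-test. This should be changed because a better method is available at little cost; it does not show that the trial will in fact be mis-sized.

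**What to change.** In Section 11 and in the synopsis under Study Population:
1. Delete the use of the observed interim effect to size the trial.
2. State now the smallest difference in volume change worth detecting, with the significance level and power. This is a judgement about what would matter to patients, so it can be made even though the response cannot be forecast.
3. At the interim, re-estimate only the SD of volume change from all subjects together. Subjects and investigators learn the allocation at week 20, so say explicitly that the calculation must not use it.
4. Recompute the size from that SD with 60 as the cap. If the recomputed size exceeds 60, report the power that 60 gives.

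The cost is one paragraph in Section 11 and a matching sentence in the synopsis. The sponsor must commit to a target difference and gives up shrinking the trial on an early large effect. The pooled SD slightly overstates the size (about 10% at 0.8 SD), which errs on the safe side. With the cap, the method can keep or reduce the size but cannot rescue a need well above 60, such as 141 at 0.5 SD; it would make that shortfall visible.
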